potential differences between ET+RT vs. RT+ET. Additionally, delta changes (Δ) from pre-post were calculated to SBP, DBP, MAP, HR, and PP outcomes to test by the independent Student *t*-test differences between groups, where optionally the non-parametric Wilcoxon test was applied for non-parametric variables. The Cohen *d* effect size was obtained with threshold values at 0.20, 0.60, 1.2, and 2.0 for small, moderate, large, and very large effects, respectively²⁸. These analyses were carried out by the statistical software Graph Pad Prism 8.0 software (Graph Pad Software, San Diego, CA, USA). After this, all results in Δ changes of the sum of SBP $\sum\Delta$ SBP was individualized and presented in quartile to be categorized in those participants ‘nonresponders’ (NRs; Q1 with SBP < -1 mmHg), ‘low’ responders (LRs; Q2 with SBP -1 to -9.9 mmHg), ‘moderate’ responders (MRs; Q3 with SBP -10 to -18 mmHg), and ‘high’ responders (HRs; Q4 with SBP \geq -18 mmHg) according with their blood pressure changes (*i.e.*, particularly decreases) as previously have been reported²⁹. Linear regression was applied in the backward mode for testing those potential body composition, metabolic and physical condition outcomes predictors outcomes of the PEH. The $\sum\Delta$ SBP decreases an average of the session 1 and 2 of both ET+RT and RT+ET groups related to the PEH (*i.e.*, decreases in SBP) was used as ‘dependent’ outcome, while age, height, body mass, BMI, waist circumference, body fat in % and kg, lean mass, skeletal muscle mass, bone mass, total body water, BMR, SBP, DBP, HR at rest, pulse pressure, fasting glucose, total cholesterol, LDL-c, HDL-c cholestetrol, triglycerides, 6Mwt, and handgrip muscle strength (dominan, and non-dominant arm) were used as ‘independent’ predictors. Statistical analyses for these procedures were applied using SPSS software version 28 (SPSSTM Inc., Chicago, Illinois, USA). The alpha level was fixed at ($p < 0.05$) for all tests of statistical significance.

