**Interindividual Postexercise Hypotension Response in Morbid
Obesity**

NCT05504629

Date: March 17th, 2021

Study documents

Scientific background: Physical inactivity and sedentary behaviour [*i.e.*, Do not adhere to international physical activity guidelines of a minimum of 150 min of physical activity ^{1]} together with other lifestyle conditions (*i.e.*, unhealthy nutrition, or poor sleep time) promote obesity, and cardiometabolic diseases such as type 2 diabetes mellitus (T2DM), and arterial hypertension (HTN) ², two major diseases in the modernity, and of high prevalence in populations with excessive of adiposity such as those with morbid obesity ². Unfortunately, metabolic syndrome (MetS), another more complex cardiometabolic square that implies also obesity, poor glucose control, high blood pressure, dyslipidaemia, and high triglycerides in plasma exacerbates the risk for suffering from cardiovascular disease particularly those with morbid obesity who are candidates for bariatric surgery ³. For example, a relevant meta-analysis of 87 studies with a sample of ($n=951.083$) showed that MetS risk factors were associated with an increased risk for cardiovascular disease (CVD) (Relative Risk, [RR]= 2.35), CVD mortality (RR= 2.40), myocardial infarction (RR= 1.99, stroke (RR= 2.27), and all-cause mortality (RR= 1.58) ⁴. Patients with Morbid obesity are a particular population that suffers from multiple risks for CVD, including MetS, endothelial dysfunction, as well as HTN and T2DM risk factors, all of these related to a better or worse profile to deal with success and better recovery period after bariatric surgery ¹. From the National Health Survey of Chile, there was described that morbid obesity is a worrying concern in women in childbearing ages 20 to 45 y, showing almost no changes from 2003 (2.2%) to 2009-10 Survey (2.1%) ⁵. Thus, among these patients, to acquire the bariatric surgery benefit, these increase their possibilities to lose excess weight near to ~50%, to recover their overall cardiometabolic health ⁶, and this has been strongly related to improvements in their quality of life ⁷.

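### The responder rule cannot be applied as written: the nonresponder and high-responder limits run the wrong way, two classes share -18 mmHg, and sample quartiles are equated with fixed mmHg bands

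*Combined protocol and SAP*

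**What the plan says.** All of this is in the Statistical Analysis Plan (SAP), which has no subsections.

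- **Variable classified.** The responder sentence works on "all results in Δ changes of the sum of SBP", written with the symbol ∑ΔSBP. It does not say what is summed.
- **Grouping.** This variable "was individualized and presented in quartile to be categorized in those participants" and then given four labels.
- **Limits.** Nonresponders (NR): "NRs; Q1 with SBP < -1 mmHg". Low responders (LR): Q2, from -1 to -9.9 mmHg. Moderate responders (MR): "MRs; Q3 with SBP -10 to -18 mmHg". High responders (HR): "HRs; Q4 with SBP \geq -18 mmHg". A closing remark says that decreases in pressure are what is chiefly meant, and the classes are said to follow a cited source, "as previously have been reported".
- **Same symbol in the regression.** After a sentence introducing backward linear regression, ∑ΔSBP reappears as the dependent variable, described as "decreases an average of the session 1 and 2 of both ET+RT and RT+ET groups".

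The group sizes, 17 (ET+RT) and 13 (RT+ET), are given under Methods.

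**The concern.** The study title begins "Interindividual Postexercise Hypotension Response in Morbid", and the background justifies the study by the need for individual-level data. The responder rule is the SAP's only classification of individual patients. If the rule is ambiguous, two competent analysts can put the same patient in different classes and report different numbers of nonresponders and high responders.

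Three things looked wrong: the direction and boundaries of the limits, the double definition of each class as a quartile and as a mmHg band, and the undefined variable to which the limits apply.

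**Working it through.** The plan states no responder count or share, so there is no figure to reproduce. The check applies the printed limits to test values.

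**1. Limits.** Let x be the signed SBP change in mmHg, with a fall negative.

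- Literal reading: NR x < -1; LR -9.9 ≤ x ≤ -1; MR -18 ≤ x ≤ -10; HR x ≥ -18.
- Size-of-fall reading, with d = -x: NR d < 1; LR 1 ≤ d ≤ 9.9; MR 10 ≤ d ≤ 18; HR d ≥ 18.

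| x | Literal | Size of fall |
|---|---|---|
| +5 | HR | NR |
| 0 | HR | NR |
| -5 | NR, LR, HR | LR |
| -9.95 | NR, HR | none |
| -14 | NR, MR, HR | MR |
| -18 | NR, MR, HR | MR, HR |
| -22 | NR | HR |

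On the literal reading, every value below -18 is NR only and every value above -1 is HR only. The background cites a fall of 22.0 mmHg after resistance exercise in hypertensive subjects; the literal rule calls that a nonresponse. On the size-of-fall reading the labels fall in the intended order, and two defects remain: the overlap at -18 and the gap between -9.9 and -10. The overlap can arise with whole-mmHg values. The gap matters only if values carry more than one decimal.

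**2. Quartiles against bands.** The total is 17 + 13 = 30, and 30/4 = 7.5, so pooled quartiles hold 7 or 8 patients each. Within group, 17/4 = 4.25 gives 4 or 5, and 13/4 = 3.25 gives 3 or 4. Fixed bands reproduce such counts only if the sample quartiles lie near -1, -10 and -18. For a normal variable, quartiles at -1 and -18 require a mean of (-1 - 18)/2 = -9.5 and an SD of 8.5/0.6745 = 12.6. The documents do not say whether the data look like this.

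**3. Scale (secondary).** Suppose the sum runs over two sessions, so that sum = 2 × average. Limits of -1, -10 and -18 on the sum are then -0.5, -5 and -9 on the average. With limits read as sizes of a fall:

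- a fall of 6 in each session is LR on the average (-6) and MR on the sum (-12);
- a fall of 12 in each session is MR on the average (-12) and HR on the sum (-24).

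Illustration only: assume a normal two-session average with mean -12.0 (a value the background cites for subjects with elevated pressure after resistance exercise) and an assumed SD of 6 to 12. The HR share on the average is Φ((-18 + 12)/SD), or 16% to 31%. On the sum it is Φ((-9 + 12)/SD), or 69% to 60%. These shares require a two-session sum and fixed limits. The documents give no distribution of SBP change for this trial.

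**4. What is not touched.** The ANOVA uses absolute values and the t-tests use pre-post changes; neither uses the classes. The regression uses the continuous variable. Replacing y by 2y doubles the coefficients and their standard errors and leaves t, p, R-squared and backward selection unchanged.

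**The case against.** The strongest reply is that the rule is readable by intent. The remark that decreases are meant points to sizes of a fall, and read that way the four labels are in order. The reversed inequalities are then probably a notation slip. That stands as an account of intent, but it does not remove the overlap at -18 or the gap below 10.

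On quartiles, the text is in the past tense and pairs each quartile with one range, so the limits may simply be the observed cut-points. In that case quartiles and bands do not conflict. The plan does not say so, however, and class percentages would then be fixed by construction. The limits may instead come from the cited source, which cannot be checked from these documents.

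A reader might go further and infer that the plan contradicts itself by calling one variable both a sum and an average. The documents do not support that. The averaging is stated for the regression outcome, after an intervening sentence, and what is summed is never stated. The two descriptions can be reconciled, for example as changes summed within a session and then averaged over the two sessions. The scale is undefined; it is not shown to be inconsistent. A reader might also infer that a given share of patients is misclassified, but no such share can be derived without a distribution.

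**Conclusion.** The point holds for the classification rule. As printed, the outer limits are reversed. Read as probably intended, one boundary value is in two classes and a narrow interval is in none. These findings need no assumption beyond the printed limits. Each class is also defined in two ways that need not agree; if quartiles decide, about 25% of the 30 patients are nonresponders whatever the response.

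The undefined symbol is a secondary clarification. Its factor of 2 depends on the sum running over two sessions. The consequence is confined to the responder classes and any statement made from them. Because this is the plan's only individual-level classification in a study about individual response, the rule should be corrected.

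**What to change.** 1. Keep the plan's own limits and write them as exhaustive, non-overlapping signed bands: NR x > -1; LR -10 < x ≤ -1; MR -18 < x ≤ -10; HR x ≤ -18. State that placing -18 in HR and closing the gap between -9.9 and -10 are choices.
2. Remove Q1 to Q4 from the class definitions. If the limits are in fact the observed quartiles, say so, state whether they are pooled or within group, and do not interpret the class percentages as response rates.
3. Define ∑ΔSBP once, stating what is summed or averaged, and use the same variable and scale in the classification and the regression.

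The cost is a few lines of SAP text and a re-run of the classification table. Class sizes may change. If the definition moves between a two-session sum and average, regression coefficients rescale by 2 and the inference does not change.

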On the other hand, the main PEH studies report data in terms of ‘average data’, and it is well known that there is a wide interindividual variability to exercise training²⁷, being a need for the report of data at an individual level. Thus, considering that there is little knowledge about the role of the order (*i.e.*, starting by ET plus RT or by RT plus ET) in the CT session, taking into account that risk factors for MetS increase the risk for vascular damage and CVD. This study will follow the CONSORT guidelines for randomised trials, will be developed in accordance with the Declaration of Helsinki (2013), and has been approved by the Ethical Committee of the Universidad de La Frontera, Temuco, Chile (DI18-0043 Project, ACTA N° 080_21). **Design:** A quasi-experimental clinical study. **Methods:** Patients with morbid obesity were invited for participating by a public invitation and directly to the Morbidly Obesity Association of Temuco, City, Chile (OBEMOB). After providing wide information and feedback about the risks/benefits of the intervention, all participants signed informed consent for participating in the study. We recruited diagnosed morbid obesity sedentary/physically inactive subjects (body mass index [BMI] between ≥ 40 kg/m²; aged 30 to 55 years) that were under the OBEMOB institution, who were assigned for convenience in 1:1 allocation to a CT group of endurance [ET] plus resistance training [RT] (ET+RT; $n=17$; BMI 47.8 ± 16.7) or resistance training plus endurance training group (RT+ET; $n=13$; BMI 43.0 ± 8.0). Patients were recruited between 2020 and 2021 year from the above non-governmental mentioned institution. All participants were part of the lifestyle program

previous to the possibility of receiving the bariatric surgery benefit for this disease condition from the Health Ministry of Chile (MINSAL).

REFERENCES

3. Bellicha A, van Baak MA, Battista F, et al. Effect of exercise training before and after bariatric surgery: A systematic review and meta-analysis. *Obesity Reviews* 2021; **22**: e13296.

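### Backward regression over 24 candidates in about 30 patients is read at p<0.05 with no allowance for selection, so its surviving p-values and R² are not valid evidence of predictors of postexercise hypotension

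*Combined protocol and SAP*

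**What the plan says.** The Methods text gives two groups, "ET+RT; $n=17$; BMI 47.8 ± 16.7" and "RT+ET; $n=13$; BMI 43.0 ± 8.0".

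The SAP then specifies the predictor analysis: "Linear regression was applied in the backward mode for testing those potential body composition, metabolic and physical condition outcomes predictors". The dependent variable is the SBP fall, taken as "an average of the session 1 and 2 of both ET+RT and RT+ET groups". The candidate list begins "age, height, body mass, BMI, waist circumference, body fat in % and kg, lean mass, skeletal muscle mass, bone mass, total body water, BMR" and continues "SBP, DBP, HR at rest, pulse pressure, fasting glucose, total cholesterol, LDL-c", followed by HDL cholesterol, triglycerides, the six-minute walk and grip strength in each arm. The software is SPSS 28. Alpha is 0.05 "for all tests of statistical significance".

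For this regression the SAP gives no removal threshold, no prior reduction of the list, no shrinkage, no validation and no adjustment for selection. It does not label the analysis exploratory, and it does not say in so many words that the two groups are fitted together.

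**The concern.** Backward elimination keeps a variable because its p-value is small. Reading that same p-value at 0.05 afterwards treats the final model as if it had been fixed beforehand. The usual t-tests and R² take no account of the variables tried and discarded. With almost as many candidates as patients, the starting model has few residual degrees of freedom, and chance associations survive easily.

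At stake is what the study says about who responds. Individual response is its theme, and this is the analysis meant to find what predicts it. Noise variables could be reported as predictors, with an R² that looks substantial.

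**Working it through.** **Inputs from the documents.**
- Patients: 17 + 13 = 30 (Methods).
- Candidates: 12 from age to BMR, counting body fat in % and in kg separately. A further 7 run from SBP to LDL-c, and 5 more are HDL-c, triglycerides, six-minute walk and two grip measures. 12 + 7 + 5 = 24.
- Alpha: 0.05 for all tests.

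The plan states no false-positive rate or removal threshold, so there is no figure of its own to reproduce.

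**Pooled or by group.** The outcome wording refers to both groups, so pooling is the natural reading. With 23 predictors and an intercept there are 24 parameters, more than the 17 or 13 patients in either group. Even 12 predictors and an intercept leave 13 − 13 = 0 residual degrees of freedom in RT+ET.

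**Free predictors (assumed).** If pulse pressure is SBP minus DBP from the same resting readings, the three are linearly dependent and at most 23 candidates are free. There are fewer if, for example, body mass is the sum of fat and lean mass, or LDL-c is calculated from the other lipids. The documents do not say, so I use 12 to 23.

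**Residual degrees of freedom of the starting model**, 30 − 1 − k: 6 for k = 23, 11 for k = 18, 17 for k = 12.

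**Simple benchmark.** For k independent tests at 0.05, the chance of at least one false positive is 1 − 0.95^k: 46% for k = 12, 60% for k = 18, 69% for k = 23.

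**Simulation of the procedure.** n = 30 and the outcome is unrelated to any predictor. The largest p-value is removed until all are below the threshold, and a run counts if any survivor has p<0.05. Correlation patterns run from independent predictors to a block at r = 0.95. The 18 and 23 columns used 3,000 runs per setting (standard error at most √(0.25/3000) = 0.9 points).

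| Removal at (assumed) | 12 free, lower end | 18 free | 23 free |
|---|---|---|---|
| 0.01 | 12% | 20–25% | 25–31% |
| 0.05 | 51% | 68–74% | 78–83% |
| 0.10 | 59% | 82–87% | 91–94% |

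Median R² on pure noise is 0.37–0.42 (23 free) and 0.22–0.26 (18 free) at removal 0.05, and 0.60–0.61 and 0.38–0.41 at removal 0.10. At 0.01 it is 0, because most null runs keep nothing. A fixed null model of three predictors plus group has median R² 0.12.

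**Which test a fixed model should use.** The SAP's changes are pre to post: "delta changes (Δ) from pre-post were calculated to SBP, DBP, MAP, HR, and PP outcomes". If resting SBP is the pre-exercise reading and variances are equal, its correlation with the change is −√((1 − r)/2), where r is the pre–post correlation. For assumed r = 0.6 this is −√0.20 = −0.45; for r = 0.9 it is −√0.05 = −0.22. Regression to the mean alone then makes the SBP term p<0.05 in 67% (r = 0.6) to 21% (r = 0.9) of samples, and the overall F-test significant in 47% to 13%. The joint F-test of the other predictors, adjusted for group and SBP, stays at 5%.

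The overall F-test also tests group. With three noise predictors and an assumed group effect of 0.5, 0.8 or 1.2 SD, it rejects in 14%, 31% and 64%. The joint F-test of the predictors adjusted for group stays at 5%.

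Leaving SBP out does not remove the coupling. If a retained predictor such as DBP or pulse pressure has an assumed correlation of 0.6–0.8 with pre-exercise SBP, and r is 0.6–0.9, the overall F-test rejects in 7–28% from regression to the mean alone.

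**The case against.** The percentages rest on stacked assumptions: a removal threshold the SAP does not give, a number of free predictors it does not settle, and a complete null. A reader might infer a narrower and more alarming figure, such as 68–94%, as this study's false-positive rate. The documents do not support that. It needs removal at 0.05 to 0.10 and at least 18 free predictors, and neither is stated. Nor is the complete null the expected situation: the scientific background itself reports larger falls at higher initial pressure. The rates are a reference case. What survives is that every setting examined is above 5%.

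A reader might also infer that the starting model cannot be fitted because SBP, DBP and pulse pressure all appear. That holds only if pulse pressure is the exact difference of the other two, which the documents do not say. The main point does not need it.

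The SAP's wording about potential predictors can be read as hypothesis-generating, so an exploratory label and a stated threshold might seem enough. They would reduce the harm, but the post-selection p-values would still be invalid, and the SAP as written applies 0.05 to them without qualification.

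Finally, the SAP is in the past tense. If results have been seen, a claim to have chosen predictors on prior grounds cannot be verified, and the 5% rate of the fixed model assumes that they were. This objection stands and is met in the fix by labelling.

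**Conclusion.** The concern holds. Followed as written, the analysis gives p-values and an R² that cannot be taken as evidence of predictors of postexercise hypotension. Under a complete null with 12–23 free predictors, the chance of at least one nominally significant predictor is about 51–83% at removal 0.05, 59–94% at 0.10 and 12–31% at 0.01. These ranges depend on the assumed threshold, number of free predictors and correlation pattern; the conclusion does not.

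A reader might go further and infer that any predictor reported is false, or that the trial's other results are undermined. Neither follows. A real predictor could be among the survivors, but this procedure cannot show which. The comparison of exercise orders and the responder classes do not use this regression. It should be corrected before predictors are reported.

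**What to change.** - State that the model is pooled over both groups.
- Replace backward elimination with a fixed model: exercise-order group, resting SBP as an adjustment term, and about two or three further listed predictors, chosen on prior grounds with the reasons recorded. State whether resting SBP is the reading from which the change is calculated.
- Read first the joint F-test of the further predictors, adjusted for group and resting SBP. Do not use the overall F-test, which also picks up the group difference and the SBP coupling.
- If resting SBP is left out, give the reason and still use the joint F-test adjusted for group. Warn that DBP, pulse pressure or any other correlate of resting SBP is coupled to the SBP change; adjusting for group does not remove this.
- Define pulse pressure. If it is SBP minus DBP, do not enter all three together.
- If results have already been seen, label the fixed model post hoc.
- If all candidates are to be screened instead, use penalised regression with repeated cross-validation, report an optimism-corrected R², label the result exploratory, and do not read post-selection p-values at 0.05. If the backward model is still shown, state its removal threshold.

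The cost is SAP wording and one re-run on data already collected. Candidates outside the fixed model go untested, so a true predictor among them would be missed. Fewer significant predictors and a lower R² will be reported.

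### The predictor regression pools two convenience-formed exercise-order groups with no order term, so slopes of characteristics associated with order may be partly confounded by it

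*Combined protocol and SAP*

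**What the plan says.** The Scientific background gives exercise order as a reason for the study, since "there is little knowledge about the role of the order" within a concurrent session. Under Methods, patients are those "who were assigned for convenience in 1:1 allocation to a CT group of endurance" then resistance training (ET+RT, 17 patients) or the reverse sequence (RT+ET, 13 patients).

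In the SAP, "Linear regression was applied in the backward mode", and the outcome is the SBP change as "an average of the session 1 and 2 of both ET+RT and RT+ET groups related to the PEH". The predictors are "age, height, body mass, BMI, waist circumference, body fat in % and kg, lean mass, skeletal muscle mass, bone mass, total body water, BMR", followed by "SBP, DBP, HR at rest, pulse pressure, fasting glucose, total cholesterol, LDL-c, HDL-c cholestetrol, triglycerides, 6Mwt, and handgrip muscle strength (dominan, and non-dominant arm". That is 12 + 12 = 24 variables, none of which is group or order. No regression by group is described.

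Order is tested elsewhere in the SAP, by a group-by-time ANOVA and by a t-test on the pre-post changes. The responder classes have one set of mmHg limits. The SAP does not say whether they are shown for all patients together or by order.

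**The concern.** The factor the study varies is missing from the model meant to explain why patients differ in response. Because assignment was by convenience, nothing in the design makes patient characteristics independent of order. If order shifts ΔSBP, a characteristic that is systematically higher in one group picks up part of that shift and can look like a predictor of hypotensive response when it partly marks which sequence the patient performed. The part that is not picked up adds to residual variance and makes true predictors harder to see. The study's title is about interindividual response, so this regression bears on its main message.

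**Working it through.** The plan has no sample-size calculation, SD of ΔSBP or expected order effect, so there is no figure of its own to reproduce. Inputs from the documents: n = 17 and 13; BMI 47.8 (SD 16.7) and 43.0 (SD 8.0); alpha 0.05. Assumed: a two-sided test, order effects and group gaps in within-group SDs, and a removal threshold of p > 0.10 for backward selection.

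**1. Is the regression pooled?** The wording covers both groups in one outcome. The starting model also could not be fitted within a group: 24 slopes plus an intercept are 25 parameters, against 17 or 13 patients.

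**2. Bias in the BMI slope.** Bias = order effect × (cross-product of order and BMI) / (total sum of squares of BMI).
- Within-group sum of squares: 16 × 16.7² + 12 × 8.0² = 4462.2 + 768 = 5230.2. Pooled SD = √(5230.2/28) = 13.67.
- Standardised gap: 4.8/13.67 = 0.35.
- Between-group sum of squares: (17 × 13/30) × 4.8² = 169.7. Total = 5400.0.
- Share of the order contrast carried by BMI: 169.7/5400.0 = 0.031 (correlation 0.18).
- Cross-product: (17 × 13/30) × 4.8 = 35.4. Bias per 1 mmHg of order effect: 35.4/5400.0 = 0.0065 mmHg per kg/m².
- For assumed order effects of 2, 5 and 10 mmHg the bias is 0.013, 0.033 and 0.065 mmHg per kg/m².

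**3. Residual variance.** An order effect of 1.0 SD left out adds (17/30)(13/30) = 0.246 σ². With BMI in the model, 0.246 × (1 − 0.031) = 0.238 σ² stays in the residual.

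**4. False-positive rate, one predictor with no true effect** (simulation, 17 vs 13, 40,000 data sets per scenario):

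| Systematic gap in predictor | Order effect | Without order term | With order term |
|---|---|---|---|
| 0.35 SD (BMI) | 0.5 SD | 5% to 6% | about 5% |
| 0.35 SD (BMI) | 1.0 SD | about 7% | about 5% |
| 0.8 SD | 0.5 SD | about 7.5% | about 5% |
| 0.8 SD | 1.0 SD | about 14% | about 5% |
| 1.2 SD | 1.2 SD | about 30% | about 5% |

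**5. The same question under backward selection.** Pulse pressure is SBP minus DBP, so at most 23 of the 24 predictors are linearly independent. Residual degrees of freedom in the starting model are 30 − 1 − 23 = 6, or 5 with order added. The simulation used independent predictors with no true effect and an order effect of 1.0 SD (1,500 runs for 5 candidates, 500 for 23). The rates below are for one named predictor reaching p < 0.05.

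| Candidates | Gap in named predictor | Without order | Order forced in |
|---|---|---|---|
| 5 | 1.0 SD | 21.3% | 5.5% |
| 23 | 1.0 SD | 36.2% | 28.6% |
| 23 | 0.35 SD | 26.0% | 29.6% |

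Over all scenarios with 23 candidates, about 6 false predictors per analysis reach p < 0.05: 5.6 to 6.0 without order and 6.1 to 6.5 with it.

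**The case against.** The strongest reply has four parts.

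- **Order is tested separately.** True, so a reader would have some view of whether an order effect exists. But the ANOVA and the t-test do not adjust the predictor slopes, and the plan has no step that returns to the regression if they show a difference.
- **The only reported imbalance is small.** This stands. The BMI gap has a Welch t of 4.8/√(16.7²/17 + 8.0²/13) = 1.04, which is compatible with no systematic difference, and BMI carries about 3% of the order contrast. The other 23 characteristics are not reported by group, so their association with order is unknown.
- **The higher rates need large assumed effects.** This also stands. The SAP's own scale calls an effect of 1.2 large, and with an order effect of 0.5 SD the inflation is slight.
- **Too many candidates is the larger defect.** Agreed, but a shortened list would still be open to confounding without order.

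A reader might infer four stronger things that the documents do not support. First, that any order effect is credited to whichever characteristic happens to differ: a predictor absorbs order only in proportion to its association with order. Second, that chance imbalance among many characteristics inflates the error rate: with no systematic gap, the simulated single-predictor rate without order stays at 4.9% to 5.1% for order effects of 1.0 to 1.5 SD. Third, that the responder classes are pooled and therefore distorted: the SAP is silent on how they are tabulated, and with the printed mmHg limits applied to each patient's own change, pooling alters nobody's class. Fourth, that an order term brings error back to 5% in the SAP's actual procedure: with 23 candidates it does not.

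**Conclusion.** The concern holds in a limited form. The regression pools two non-randomised order groups without an order term. If order affects ΔSBP, slopes of characteristics systematically associated with order are partly confounded, and the remainder inflates residual error. Both conditions are needed, and the documents establish neither. For BMI the distortion would be small. For a characteristic differing by 0.8 SD, the single-predictor false-positive rate would be about 7.5% to 14% for order effects of 0.5 to 1.0 SD. These rates rest on normal data, a two-sided test and assumed effect sizes. The change is worth making because it is cheap and concerns the factor under study, but it does not by itself make the list of predictors reliable.

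**What to change.** Add to the SAP that exercise order (ET+RT vs RT+ET) enters the predictor regression as a fixed term that backward selection cannot remove, and that statements about predictors rest on the order-adjusted slopes. As a descriptive addition, show the responder classes by order (17 and 13 patients) and say so in the text.

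The variable is already recorded for every patient. The cost is one sentence and one residual degree of freedom. That is minor with a short predictor list but noticeable in the full starting model, where about 6 residual degrees of freedom fall to 5. The order term should therefore go together with a shortened, prespecified list of candidates, which is a separate change and the one that lets the adjustment do its work. The SAP is written in the past tense, so if the regression has already been run, the order-adjusted model should be refitted and reported as an added analysis.
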